10 RISK / BENEFIT ASSESSMENT

10.1 **Anticipated risks.** Describe the reasonably foreseeable risks of harm, discomforts, and hazards to the subjects and others of the research procedures. For each harm, discomfort, or hazard:

- Describe the magnitude, probability, duration, and/or reversibility of the harm, discomfort, or hazard, AND
- Describe how you will manage or reduce the risks. Do not describe data security protections here, these are already described in Question 9.6.
- Consider possible physical, psychological, social, legal, and economic harms, including possible negative effects on financial standing, employability, insurability, educational advancement or reputation. For example, a breach of confidentiality might have these effects.
- Examples of "others": embryo, fetus, or nursing child; family members; a specific group.
- Do not include the risks of non-research procedures that are already being performed.
- If the study design specifies that subjects will be assigned to a specific condition or intervention, then the condition or intervention is a research procedure - even if it is a standard of care.
- Examples of mitigation strategies: inclusion/exclusion criteria; applying appropriate data security measures to prevent unauthorized access to individually identifiable data; coding data; taking blood samples to monitor something that indicates drug toxicity.
- As with all questions on this application, you may refer to uploaded documents.

- Fingerstick: The fingerstick for blood collection may cause a small amount of pain or bruising, and the site may bleed slightly after collection. The study staff will follow standard procedures for collecting blood specimens from participants and attempt to minimize any chance for discomfort or bruising.
- Sensitive Information: The survey will ask questions about drug use and sexual practices. Participants could experience some discomfort while taking the survey, due to the sensitive nature of some of the questions. Participants will be encouraged to find a private space they can take the surveys. Surveys will also be de-identified.

In particular, the study surveys ask about depression, including whether participants have had thoughts that they would be better off dead or hurting themselves. This is a question in the Patient Health Questionnaire 9 (PHQ-9), which is a validated and widely used survey to screen for depression. The study surveys will be completed online and not at the study clinic. We therefore will not be able to reply in person to responses indicating that a participant wants to hurt themselves. If people report this on a study survey, we will build in a skip pattern so that the King County Crisis Line number becomes available to them. All clinical and study staff will be aware of the King County Crisis Line and other local resources that can be provided to participants if they indicate that they are experiencing depression or suicidality. If a participant contacts the study team (PI, study coordinator, or peer) indicating that they are experiencing depression or suicidality the study team member will provide appropriate referrals. The study team members will receive training on how to provide these referrals. Study site staff have experience responding to the varied needs and requests of their patients/clients and have their own clinic trainings and processes to appropriately respond to requests, including for referrals for mental health concerns.

It is possible that we will learn about child or elderly abuse or intent to harm oneself or others. If we learn about child or elder abuse or an intent to hurt someone else, we will call the police non-emergency number.

- Loss of confidentiality: The study staff will do everything possible to keep participants' information private; however, there is always the risk of a breach of confidentiality. All identified study documents will be kept in a locked cabinet in the principal investigator's locked office. De-identified study records will be stored in a locked cabinet at the research coordinators' desk and on work computers that are password-protected and encrypted. Participants' phone numbers will be stored in the secure text platform to communicate with participants, and their email will be stored in the survey platform to send links to study surveys.

All members of the research team are responsible for the security and protection of research records. Procedures of preventing breaches of confidentiality include regular Collaborative Institutional Training Initiative (CITI) training of all study staff, collecting minimum necessary identifiers, limiting access to identifiers, encrypting devices, and using coded data. If there is a breach of confidentiality, we will report this to the IRB as an unanticipated problem within 24 hours and will address the breach to a degree that is dependent on the extent and impact of the breach. Consequences may include staff retraining, changing of staff responsibilities, up to dismissal of study staff for serious violations.

- Unsecured communication: There is also a risk of unsecured communication for the participants who are assigned to receive peer support. The peer will communicate with participants via phone, email, and text. Because unencrypted email, text messaging, and phone conversations are unsecured, there is a risk that this correspondence could be intercepted by a third party. In order to mitigate these risks, we will correspond with their participants in the way they choose, explain these risks in the consent form, and talk with them about ways to reduce these risks (e.g. using an encrypted app on both phones, deleting messages after they receive them, looking at messages in a private setting).

New activities for all MSM/TGP” and “New activities for PrEP providers, (prescribers, caseworkers and peer educators/navigators, etc):

- Sensitive Information: The interview will ask questions about drug use and sexual practices. Participants could experience some discomfort while participating in the interview, due to the sensitive nature of some of the questions. Participants will be encouraged to find a private space where they can speak freely during the interview. Interviews will also be de-identified.
- Loss of confidentiality: The study staff will do everything possible to keep participants' information private; however, there is always the risk of a breach of confidentiality. All identifiable contact information (participant name, email and/or phone number) will be kept in a locked cabinet in the principal investigator's locked office. De-identified study records (the demographic surveys asked at the end of the interview) will be stored in a locked cabinet at the research coordinators' desk and on work computers that are password-protected and encrypted.

All members of the research team are responsible for the security and protection of research records. Procedures of preventing breaches of confidentiality include regular Collaborative Institutional Training Initiative (CITI) training of all study staff, collecting minimum necessary identifiers, limiting access to identifiers, encrypting devices, and using coded data. If there is a breach of confidentiality, we will report this to the IRB as an unanticipated problem within 24 hours and will address the breach to a degree that is dependent on the extent and impact of the breach. Consequences may include staff retraining, changing of staff responsibilities, up to dismissal of study staff for serious violations.

10.2 Reproductive risks. Are there any risks of the study procedures to men and women (who are subjects, or partner of subjects) related to pregnancy, fertility, lactation or effects on a fetus or neonate?

Examples: direct teratogenic effects; possible germline effects; effects on fertility; effects on a woman's ability to continue a pregnancy; effects on future pregnancies.

	No
	Yes

→ If no go to [question 10.3](#)

→ If yes, answer the following questions:

a. **Risks.** Describe the magnitude, probability, duration and/or reversibility of the risks.

b. **Steps to minimize risk.** Describe the specific steps you will take to minimize the magnitude, probability, or duration of these risks.

Examples: inform the subjects about the risks and how to minimize them; require a pregnancy test before and during the study; require subjects to use contraception; advise subjects about banking of sperm and ova.

If you will require the use of contraception: describe the allowable methods and the time period when contraception must be used.

c. **Pregnancy.** Describe what you will do if a subject (or a subject's partner) becomes pregnant

For example; will you require the subject to immediately notify you, so that you can discontinue or modify the study procedures, discuss the risks, and/or provide referrals or counseling?

10.3 Unforeseeable risks. Are there any research procedures that may have risks that are currently unforeseeable?

Example: using a drug that hasn't been used before in this subject population.

	No
	Yes

→ If yes, identify the procedures.

10.4 Subjects who will be under regional or general anesthesiology. Will any research procedures occur while subjects-patients are under general or regional anesthesia, or during the 3 hours preceding general or regional anesthesia (supplied for non-research reasons)?

	No
	Yes

→ If yes, check all the boxes that apply.

Administration of any drug for research purposes

Inserting an intra-venous (central or peripheral) or intra-arterial line for research purposes

Obtaining samples of blood, urine, bone marrow or cerebrospinal fluid for research purposes

Obtaining a research sample from tissue or organs that would not otherwise be removed during surgery

Administration of a radio-isotope for research purposes**

Implantation of an experimental device

Other manipulations or procedures performed solely for research purposes (e.g., experimental liver dialysis, experimental brain stimulation)

If you checked any of the boxes:

You must provide the name and institutional affiliation of a physician anesthesiologist who is a member of your research team or who will serve as a safety consultant about the interactions between your research procedures and the general or regional anesthesia of the subject-patients. If your procedures will be performed at a UW Medicine facility or affiliate, the anesthesiologist must be a UW faculty member.

*** If you checked the box about radio-isotopes: you are responsible for informing in advance all appropriate clinical personnel (e.g., nurses, technicians, anesthesiologists, surgeons) about the administration and use of the radio-isotope, to ensure that any personal safety issues (e.g., pregnancy) can be appropriately addressed. This is a condition of IRB approval.*

10.5 Data and Safety Monitoring. A Data and Safety Monitoring Plan (DSMP) is required for clinical trials (as defined by NIH). If required for your research, upload your DSMP to the **Supporting Documents** SmartForm in **Zipline**. If it is embedded in another document you are uploading (for example, a Study Protocol, use the text box below to name the document that has the DSMP.

In response to the study sponsor's request we have formed a DSMB for this study. The DSMB will meet prior to the start of the study to review the protocol and annually until study completion. The Data Safety and Monitoring Plan (DSMP) that is uploaded to the Supporting Document SmartForm supersedes the DSMP that was originally proposed in the Funding Application.

10.6 Un-blinding. If this is a double-blinded or single-blinded study in which the participant and/or you do not know the group to which the participant is assigned: describe the circumstances under which un-blinding would be necessary, and to whom the un-blinded information would be provided.

10.7 Withdrawal of participants. If applicable, describe the anticipated circumstances under which participants will be withdrawn from the research without their consent. Also, describe any procedures for orderly withdrawal of a participant, regardless of the reason, including whether it will involve partial withdrawal from procedures and any intervention but continued data collection or long-term follow-up.

While the study team will do their best to retain all participants for the duration of the study, it is possible that participants will discontinue their participation early, before the final 6-month visit. This could occur due to participant choice, study team decision, or experiencing an adverse event (AE). If someone has an AE related to PrEP and is willing to remain in the study, we will discontinue PrEP in that participant, but continue to follow them to monitor the AE and its resolution. If someone exits the study early, we will attempt to schedule a final visit that will include the same procedures as a scheduled month 3 or 6 visit. If a participant refuses to return for a final visit, we will ask them to at least complete an exit CASI. Reasons for early discontinuation will be recorded on study data collection forms.

In addition, the study team will discontinue participants if they do not complete a baseline CASI within 7 days (with the exception of extenuating circumstances) of their entry visit, in which case they will be replaced. If the study team thinks that the participation of a study participant could cause harm to them or the study

staff (e.g., inappropriate, aggressive behavior), the study team may end participation for that participant early. We do not expect this to occur.

10.8 Anticipated direct benefits to participants. If there are any direct research-related benefits that some or all individual participants are likely to experience from taking part in the research, describe them below:

Do not include benefits to society or others, and do not include subject payment (if any). Examples: medical benefits such as laboratory tests (if subjects receive the results); psychological resources made available to participants; training or education that is provided.

For participants assigned to the peer navigation group, we expect that they may benefit from receiving peer support to take their PrEP and having assistance with other needs they may ask for help with.

10.9 Individual subjects findings.

a. Is it likely that your research will unintentionally discover a previously unknown condition such as a disease, suicidal intentions, or genetic predisposition?

	No
	Yes

→ If yes, explain whether and how you would share the information with the subject.

[Redacted]

b. Do you plan to share the individual results of any of your study procedures or findings with the subjects – such as genetic test results, laboratory tests, etc.?

You should answer YES if your consent form says anything about sharing individual information with subjects.

	No
	Yes

→ If yes, complete and upload the [SUPPLEMENT: Participant Results Sharing](#) to the [Supporting Documents](#) SmartForm of [Zipline](#)

10.10 Commercial products or patents. Is it possible that a commercial product or patent could result from this study?

	No
	Yes

→ If yes, describe whether subjects might receive any remuneration/compensation and, if yes, how the amount will be determined.

[Redacted]

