- Involves having the subjects use a drug, biological, botanical, nutritional supplement, or medical device.

"Minimal risk" means that the probability and magnitude of harm or discomfort anticipated in the research are not greater than those ordinarily encountered in daily life or during the performance of routine physical or psychological examinations or tests.

a. **Background.** Provide the rationale and the scientific or scholarly background for your proposed activity, based on existing literature (or clinical knowledge). Describe the gaps in current knowledge that your project is intended to address.

This should be a plain language description. Do not provide scholarly citations. Limit your answer to less than one page, or refer to an attached document with background information that is no more than three pages long.

There is an urgent need to find ways to successfully target HIV prevention strategies to cisgender men and transgender individuals who have sex with men (MSM/TG) who use methamphetamine (meth). Meth-using MSM/TG are at particularly high risk for HIV acquisition. Public Health – Seattle King County (PHSKC) has estimated that MSM/TG who use meth are 5 times more likely to be diagnosed with HIV than non-meth using MSM/TG. Daily, oral pre-exposure prophylaxis (PrEP) with Truvada is a highly-effective strategy for the prevention of HIV in adults and its use is increasing in Seattle and the United States. However, despite overall increases in PrEP use, high HIV risk among meth-using MSM/TG, and high interest in PrEP among MSM/TG, there is a smaller than expected number of meth-using MSM/TG who are enrolling in local PrEP programs. Effective HIV prevention efforts will need to decrease barriers to PrEP uptake and better target PrEP delivery to meth-using MSM/TG.

In addition, MSM/TGP who use meth and have initiated PrEP often have challenges with persistence and adherence. Importantly, PrEP's efficacy is related to adherence, and if people take too few pills or discontinue PrEP they receive limited or no benefit from it and can be at risk for HIV infection. Work is needed to monitor and support adherence among meth-using MSM/TG who initiate PrEP.

Building on our preliminary work, we plan to develop and pilot interventions for meth-using MSM/TGP with potential to be cost-effective, scalable, and easily adaptable. Peer navigation has been studied in antiretroviral (ARV) treatment and has been proposed for PrEP.

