3 NON-UW RESEARCH SETTING

Complete this section only if your research will take place outside of UW and Harborview

3.1 Reason for sites. Describe the reason(s) why you selected the sites where you will conduct the research.

We will still operate the study out of Gay City and Kelley-Ross pharmacy, and the reasons for selecting those sites are below. At this time we propose to broaden study sites to any provider or organization in King County who provides PrEP to someone who is eligible (for example, Madison Clinic at Harborview, Public Health King County STD clinic, private practitioners) and contacts us if the person is interested in participating. During the

first few months of this study we have seen a very small number of eligible people at Gay City and Kelley-Ross (recent methamphetamine use and seeking PrEP). We have brainstormed and asked community partners regarding approaches to broaden our reach to engage with more individuals who may be eligible and interested to enroll in the study. We have provided study information to colleagues and community partners and believe that some may have persons who seek PrEP from them and would be interested in participating in this study. Furthermore, aside from the consent process and fingerstick dried blood spot collection all research procedures (e.g., peer navigation, surveys) are done outside of the study site.

We selected two non-UW sites to participate in this study: Gay City and Kelley-Ross. These sites were selected for several reasons. First, both Gay City and Kelley-Ross have dedicated PrEP clinics, where meth-using MSM/TG (the target population) seek PrEP. Second, the UW research team has existing relationships with both clinic's leadership, and the PI, [name], is the Medical Director and PrEP provider at Gay City. Finally, in the surveys we did as part of study #54, we asked meth-using MSM/TG where they would like to access PrEP and both Gay City and Kelley-Ross were in the top half in both surveys with 33% saying they would like to get PrEP at Gay City and 27% saying Kelley-Ross in our final survey.

3.2 Local context. Culturally-appropriate procedures and an understanding of local context are an important part of protecting subjects. Describe any site-specific cultural issues, customs, beliefs, or values that may affect your research or how it is conducted.

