5 PROCEDURES

5.1 Study procedures. Using lay language, provide a complete description of the study procedures, including the sequence, intervention or manipulation (if any), drug dosing information (if any), use of records, time required, and setting/location. If it is available and you think it would be helpful to the IRB: Upload a study flow sheet or table to the **Supporting Documents** SmartForm in **Zipline**.

For studies comparing standards of care: It is important to accurately identify the research procedures. See UW IRB [POLICY: Risks of Harm from Standard Care](#) and the draft guidance from the federal Office of Human Research Protections, ["Guidance on Disclosing Reasonably Foreseeable Risks in Research Evaluating Standards of Care"](#); October 20, 2014.

This research study will be conducted in addition to standard of care procedures for PrEP use. Therefore, clinical procedures, including blood draws for laboratory testing, STI screening, PrEP prescriptions, and adherence counseling will be performed in accordance with the clinic's standard of care. Participants will be followed in this study and have visits at entry (baseline), and then at months 1, 3 and 6.

The research procedures, in addition to informed consent, that all participants will get in addition to the standard of care, are the following:

- Randomization: After consent has been obtained the clinical site will send documentation of eligibility (checklist) and the signed informed consent, HIPAA authorization, and ROI to the study team at UW. The site will either email the documents or provide them in person to a study team member. Once these documents are received, the research coordinator will send the participant a link to the baseline survey. After completion of the baseline survey, the participant will be randomized to one of the two intervention groups: standard of care, or peer navigation. The research coordinator will open a sequentially numbered, sealed envelope with the study allocation (generated by site using blocked randomization with variable block sizes and random number generator). They will record the treatment assignment of the participant in their de-identified chart and send a text or email to inform the participant of their assignment.

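### Section 10.7 stops PrEP after any PrEP-related adverse event in a participant who stays in the study; read literally, this conflicts with section 5.1, which leaves prescribing to the clinic

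*Protocol*

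**What the plan says.** Section 10.7 of the protocol deals with withdrawal. It first notes that participants may leave before the 6-month visit: "This could occur due to participant choice, study team decision, or experiencing an adverse event (AE"). The next sentence sets the rule in question: "If someone has an AE related to PrEP and is willing to remain in the study, we will discontinue PrEP in that participant", while follow-up goes on so that the event and its course can be tracked.

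Section 5.1 describes the research as an addition to ordinary PrEP care. It says that "PrEP prescriptions, and adherence counseling will be performed in accordance with" the clinic's standard of care.

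Section 10.5 adds that "The Data Safety and Monitoring Plan (DSMP) that is uploaded to the Supporting Document SmartForm supersedes the DSMP" proposed in the funding application. That plan is a separate document and is not shown.

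**The concern.** The 10.7 sentence has two conditions only: the AE is related to PrEP, and the person is willing to stay in the study. It gives no grade, seriousness or duration, and no role for clinical judgement. A site that follows it as written would stop PrEP for a mild side effect, even where its own practice would be to manage the side effect and carry on.

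What is at stake is loss of HIV protection. Section 1.8.a states that "Meth-using MSM/TG are at particularly high risk for HIV acquisition" and that, if people miss too many doses or "discontinue PrEP they receive limited or no benefit from it and can be at risk for HIV infection". An unnecessary stop would work against what the study is trying to support.

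**Working it through.** No arithmetic applies. The protocol gives no figure that the point depends on, so the check sets the passages side by side.

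**Who decides about PrEP.**
- Section 5.1: the clinic, under its standard of care.
- Section 5.7.a: side effects, prescriptions and any stopping of PrEP with its reason are items to be read from the clinical chart. This fits a decision made by the clinic and recorded there.
- Section 10.7: the study's "we" stops PrEP, with no option to continue.

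**Where the two rules agree and where they do not.**

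| Situation | Section 10.7 as written | Section 5.1 | Conflict? |
|---|---|---|---|
| PrEP-related AE, clinic would stop PrEP, participant stays | Stop | Stop | No |
| PrEP-related AE, clinic would manage it and continue, participant stays | Stop | Continue | Yes |
| PrEP-related AE, participant leaves the study | Sentence does not apply | Clinic decides | No |

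The conflict is confined to the second row. The protocol does not say what the clinics' standard of care is after a PrEP-related AE, so it does not show how often that row would occur.

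**Whether the rule is qualified elsewhere.** The protocol as shown contains no AE grade, seriousness criterion or statement of prescriber discretion that limits the 10.7 sentence. The DSMP could hold one, but the 10.7 sentence does not refer to it.

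**Who "we" is.** Section 12.2 names the study team as the principal investigator, the research coordinator and the peer navigator. The investigator prescribes PrEP at one site (sections 4.3 and 8.2.d), so there "we" can be the treating clinician. The protocol also uses "we" for acts carried out at the clinic: section 5.1 for the fingerstick, and section 9.1 for screening and consent. "We" may therefore include site prescribers, but even then the sentence offers no choice except to stop. The wording fits least well where the prescriber is outside the team, since section 3.1 proposes to "broaden study sites to any provider or organization in King County who provides PrEP".

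**Size.** The one figure in the protocol that bears on the stakes is background risk, in section 1.8.a: people in this population are estimated to be "5 times more likely to be diagnosed with HIV than non-meth using MSM/TG". It describes the population and does not measure the effect of this rule.

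**The case against.** The strongest reply is context. Section 10.7 answers a form question about withdrawal, including withdrawal from an intervention while data collection continues. The sentence before the rule names an AE as one cause of early exit. A condition about being willing to remain makes most sense for someone whose participation would otherwise end. On that reading, the sentence says only that when a PrEP-related event would take someone out of the study, PrEP stops and follow-up continues. This is plausible and may be what was meant, but the sentence does not say it, and a site has only the sentence to act on.

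Three further replies stand in part:
- The conflict exists only for events where the clinic would continue PrEP, and the protocol does not describe clinic practice after an AE.
- Thresholds may be in the DSMP. Whether sites lack a clear rule altogether cannot be judged from this document.
- At outside providers, nothing shows that the study team could stop another clinician's prescription, so the practical route to harm there is weak.

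A reader might infer more than the protocol supports:
- **That the study overrides clinicians at every site.** The document describes no means of doing so, and section 5.1 points the other way.
- **That the rule biases the comparison of the arms**, for example through the drug levels in dried blood spots. The rule makes no distinction by arm, and no PrEP-related AE rate is given from which any difference could be derived.
- **That the fivefold figure shows the harm of stopping PrEP.** It compares people who use methamphetamine with those who do not.

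**Conclusion.** The point holds as a minor wording correction on participant safety. Section 10.7 states a stopping rule without any condition on severity or judgement. Read literally, it contradicts section 5.1 for any PrEP-related AE that the clinic would manage while continuing PrEP. It is a matter of what the protocol states, and not of detail left to an analysis plan.

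The conclusion rests on two assumptions: that such events can occur under the clinics' standard of care, and that no threshold in the DSMP already limits the sentence. If the authors meant only events that would otherwise end participation, the intent is narrower than the text, and the text should say so. No effect size and no bias between arms is claimed.

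**What to change.** Replace the 10.7 sentence with wording such as:

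> After an AE related to PrEP, the treating prescriber will decide whether to continue, interrupt or stop PrEP, under the clinic's standard of care and any threshold in the DSMP. A participant who is willing to stay in the study will be followed until the AE resolves, whether or not PrEP is stopped.

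This keeps the participant's willingness to stay as the condition for follow-up, agrees with section 5.1, and defers to the DSMP if it sets limits.

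The cost is one amended sentence. No visit, form or participant is added, and no new data item is needed, because section 5.7.a already takes side effects and the reason for stopping PrEP from the chart. The downside is that clinics may differ in when they stop PrEP.
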